15.4. Adverse event causality assessment

For each serious and non-serious adverse event, the investigator is required to assess the possible relationship between the adverse event and each study drug(s)/IMP(s) (i.e. **to determine whether**

there exists a reasonable possibility that the study drug caused or contributed to the adverse event). This means that there are facts (evidence) or arguments to suggest a causal relationship.

To help investigators with the decision binary tree yes/no (i.e. Related/Not related) in the evaluation of causality, the Council for International Organizations of Medical Sciences (CIOMS VI) group recommends that investigators be asked to consider the following before reaching a decision:

- Medical history (including presence of risk factors)
- Lack of efficacy/worsening of existing condition
- Study medications
- Other medications (concomitant or previous)
- Withdrawal of study medication, especially following trial discontinuation / end of study medication
- Erroneous treatment with study medication (or concomitant)
- Protocol-related procedure

The terms for reporting are:

- **Definitely Related**. The adverse event and administration of study agent are related in time, and a direct association can be demonstrated.
- **Probably Related**. The adverse event and administration of study agent are reasonably related in time, and the adverse event is more likely explained by study agent than other causes.
- **Possibly Related**. The adverse event and administration of study agent are reasonably related in time, and the adverse event can be explained equally well by causes other than study agent.
- **Probably not related** A potential relationship between study agent and the adverse event could exist (i.e., the possibility cannot be excluded), but the adverse event is most likely explained by causes other than the study agent.

Not Related. The adverse event is clearly explained by another cause not related to the study agent.

15.5. Exposure during pregnancy

All female participants of child-bearing capacity should be counseled about not becoming pregnant while on study.

Pregnancy tests are required for subjects who are classified as women of child bearing potential during the study: prior to treatment initiation, and at each visit during the treatment period (12 weeks for non-cirrhotic and 24weeks for cirrhotic patients) and 4 weeks post treatment.

If a participant has a positive pregnancy test during study participation, the site should perform the following procedures:

- The participant should immediately discontinue the study drug.
- The pregnancy should be reported to the DNDi EAE team within 72 hours of awareness of the pregnancy. Record pregnancy using the pregnancy surveillance form and submit to DNDi/EAE group and Data Management Center within 72 hours of awareness of pregnancy.
- Participant should remain on the study and should be followed up for safety concerns as per the regular visit schedule until the outcome is determined (e.g. birth, premature termination etc).
- Once the outcome has been determined, the status of the mother and infant should be recorded using the pregnancy surveillance form.
- It is requested that the investigator ask the parents to return to clinic for a follow-up on infant exposed to the study treatment in utero until they reach 24 months of age. (Child surveillance form to be used).

- Pregnancy complications and elective terminations for medical reasons/SAEs of new born should be reported as an AE or SAE, as appropriate. Elective terminations should also be reported on the pregnancy surveillance form.
- Spontaneous abortions MUST be reported as an SAE and reported on the EAE form and pregnancy surveillance form.

16.1. Sample size determination

A WHO publication^[71] describes the ideal HCV treatment as having efficacy \geq 85% in all populations in a public health setting, while DNDi's target product profile sets an acceptable real world effectiveness target of \geq 80% with 12 weeks' treatment for non-cirrhotics and 24 weeks for those with compensated cirrhosis.

16.1.1. Sample size determination for stage 1

Stage 1 of this study will be intended to give a clear indication of likely real world effectiveness. It is recognised that some sub-groups of HCV patients are more difficult to cure than others. This includes those with cirrhosis (particularly when infected with genotype 3 virus), those co-infected with HIV and those who have failed previous treatment. Within these categories, only subjects with decompensated cirrhosis and those with prior treatment with an NS5A inhibitor will be excluded. No restrictions will be imposed on the number of subjects in each sub-group and subjects with more than one of the difficult to treat characteristics (for example treatment experienced, GT3, and with compensated cirrhosis) can be enrolled. As a consequence, it is not expected that the efficacy in this study to reach the levels that could be achieved in studies with much tighter inclusion criteria. Based on published results for other treatments, we considered that the overall SVR12 rate should be superior to 85%. A sample size of 300 subjects in Stage 1 will ensure that the width of the exact Clopper-Pearson 95% confidence interval (CI) around the overall SVR12 rate expected to be observed is as small as 6-7% (see table below). It would provide over 86% power to detect at least 6% improvement in the overall SVR12 rate from this pre-specified performance goal of 85%, using a two-sided exact one-sample binomial test at a significant level of 0.05. With this sample size, the lower bound of the 95% CI will be greater than 85% if the observed overall SVR12 rate is 90% or higher.

16.1.2. Sample size determination for stage 2

As there are no changes to the design for Stage 2, a further 300 subjects will be recruited in Stage 2. The objective of Stage 2 is to provide further data on the efficacy and safety of SOF-RDV in all key subgroups. Additional subjects will be enrolled in order to reach ideally 50 subjects per subgroup (30 for GT2) when combining both stages.

If recruitment of some sub-groups proves very slow, we will adjust recruitment of other sub-groups to achieve the target of 300 subjects for stage 2 within a reasonable timeframe. This is most likely to apply to GT2.

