4.2. Schematic diagram of study design

4.3. Study duration and duration of subject participation

Study duration for the subject:

12/24 weeks on-treatment for non-cirrhotic/cirrhotic patient

+ 24 weeks post-treatment follow-up

Total = 36/48 weeks for non-cirrhotic/cirrhotic patient

+ additional long term follow-up of 6 months for subset of cured patients: total of about 16/19 months for such non-cirrhotic/cirrhotic patients

or

+ additional long term follow-up of 30 months for all patients with virological failure: total of about 40/43 months for such non-cirrhotic/cirrhotic patients

Study duration stage 1:

Actual first enrollment: October 2016 in Malaysia, April 2017 in Thailand Actual last visit completed (Follow-up visit Week 24): April 2018 Study duration stage 2: Actual first enrollment: January 2019 in Malaysia, August 2019 in Thailan

Actual first enrollment: January 2019 in Malaysia, August 2019 in Thailand Estimated last visit completed (end of long term follow-up): up to Q4 2023

5. Selection of subjects

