16.1.3. Sample size determination for the global study

A total sample size of 600 patients will ensure that the width of the 95% CI around the overall SVR12 rate expected to be observed will be as small as 4-5% (see Figure 3). With this sample size, the lower bound of the 95% CI will be greater than 85% if the observed overall SVR12 rate is 88% or higher.

Figure 3: Confidence intervals for expected observed SVR12 rates in 300 and 600 subjects				
Observed overall	N=300		N=600	
SVR12 rate	95% CI	Width of 95% CI	95% CI	Width of 95% CI
87%	82.7% to 90.6%	7.9%	84.0% to 89.6%	5.6%
88%	83.8% to 91.4%	7.6%	85.1% to 90.5%	5.4%
89%	84.9% to 92.3%	7.4%	86.2% to 91.4%	5.2%
90%	86.0% to 93.2%	7.2%	87.3% to 92.3%	5.0%
91%	87.2% to 94.0%	6.8%	88.4% to 93.2%	4.8%
92%	88.3% to 94.8%	6.5%	89.5% to 94.0%	4.5%
93%	89.5% to 95.6%	6.1%	90.7% to 94.9%	4.2%
94%	90.7% to 96.4%	5.7%	91.8% to 95.8%	4.0%
95%	91.9% to 97.2%	5.3%	92.9% to 96.6%	3.7%

The study population will comprise up to 50% subjects with compensated cirrhosis. Based on preliminary site assessment, HIV/HCV co-infected subjects will represent approximately 30% of the study population. It is expected that 35-40% of the subjects will be infected by HCV genotype 3, 35-40% genotype 1, 15-20% genotype 6 and 5-10% genotype 2. In addition, a substantial fraction of the subjects may not be treatment naïve, and may have been previously exposed to interferon/ribavirin.

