		Section 7.1; schedule of visits and study assessments for non-cirrhotic subjects changed:
		Treatment Visit Week 12 (End of Treatment or premature discontinuation) ± 7 days (added in study procedure: 12 leads ECG)
		Follow up Week 12 (-1 day and +28 days) (added in study procedure: CD4 Count)
		Follow up Week 24 (-3 days and +28 days) (added in study procedures: Symptom directed assessment, HCV RNA, Stored Plasma and dried blood spots (DBS), Chemistries (liver function test [LFT], Bili-D/ID, ALT/ AST, Serum Creatinine (not required for SVR24 only), Coagulation Markers (INR).
		Section 7.2; schedule of visits and study assessments schedule of events for cirrhotic subjects changed:
		Treatment Visit Week 24 (end of Treatment Premature discontinuation) ± 7 days (added in study procedure: 12 leads ECG)
		Follow up Week 12 (-1 days and +28 days) (added in study procedure: CD4 Count)
		Follow up Week 24 (-3 day and +28 days) (added in study procedures: Symptom directed assessment and Child Pugh Scores, HCV RNA, CD4 Count, Stored Plasma and DBS, Chemistries (LFT, Bili-D/ID, ALT/ AST, Serum Creatinine (not required for SVR24 only), Coagulation Markers (INR).
		Section 9.2.7. planned interim analysis changed:
		The interim analysis will proceed in two steps:
		Step 1: Assessing if the response rate in the most difficult to treat population of subjects infected by Genotype 3 with cirrhosis (Genotype 3-F4; approximately 50 subjects), is similar to the response rate in the rest of the population (non-Genotype 3-F4; approximately 250 subjects).
		Step 2: Deciding if the study should proceed as planned with the enrolment of 300 more subjects to receive RDV-SOF, or should be amended to allow comparison with a potent pan-genotypic reference regimen, like SOF + daclatasvir or SOF/velpatasvir.
2 nd		Synopsis; study period updated:
the protocol		Planned date of last visit completed for interim analysis: SVR4: July 2017, SVR12: November 2017

Amendment number	Release date	Purpose of amendment (key changes)
Malaysia: version 4.1	29 May 2017	Planned enrolment restart after interim analysis: December 2017
amendment 2		Planned enrolment duration for the second stage of the study: Up to 6 months
version 4.2	29 May 2017	Planned date of last visit completed: March 2019
		Final report: June 2019
		Sections 7.1 and 7.2; schedule of events for cirrhotic and non-cirrhotic subjects updated:
		Added 'X' in Follow up Week 24 in Conc. Medication Review and AE review

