		with an NS5A inhibitor were excluded. No restrictions were imposed on the number of subjects in each sub-group and subjects belonging to more than one of the difficult to treat categories were enrolled. Therefore, the efficacy in this study was not expected to reach the levels that could be achieved in studies with much tighter inclusion criteria. Based on published results for other treatments, it was considered that the overall SVR12 rate should be superior to 85% instead of the original 90% and an amendment was submitted accordingly (protocol v4.2, 05-October-2017 amendment 3). This 85% cut off point is also in line with a WHO publication that describes the ideal HCV treatment as having efficacy ≥85% in all populations in a public health setting.
		Throughout the protocol;
		The addition of and explanation of Stage 2, including an additional explanation of Stage 2 statistical analysis
		Section 5.6; Assessment of efficacy updated:
		 Sustained Virologic Response 4 weeks and 24 weeks after end of Study Drug Treatment (SVR4 and SVR24) will be evaluated in order to provide a comprehensive view of the time course of reduction in viral load
4 th		Sponsor:
protocol	04 Sep 2018 16 Nov 2018	Ministry of Public Health Thailand was added on page 1.
		Protocol synopsis and study timelines section 4.4:
Malaysia: version 5.1*		The study timelines are revised
version 6.0*		Protocol synopsis and 3.2 secondary objectives:
Thailand:		 Secondary Objective
version 5.0	20 Dec 2018	To evaluate the presence of viral resistance-associated variants (RAVs) to SOFRDV at the time of failure or at first point after failure when viral load is sufficient to get a positive result in patients with virological failure and their persistence until 1 year after treatment cessation or the initiation of an alternative HCV therapy.
		Protocol synopsis and 3.3 exploratory objectives:
		 Exploratory objective
		To evaluate the effect of drug use, as determined by hair analysis on safety and efficacy (Stage 1 only)
		To assess the occurrence of drug use in virological failures (both stages)
		Protocol synopsis: Planned number of patients:
		% of cirrhotic patients: Previous wording: the study population will comprise up to 30% subjects with compensated cirrhosis.

Amendment number	Release date	Purpose of amendment (key changes)

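### The 85% SVR12 goal that section 16.1.1 calls pre-specified for Stage 1 was 90% until amendment 3 lowered it on 5 October 2017, while Stage 1 SVR12 outcomes were accruing

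*Protocol*

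**What the plan says.** Section 16.1.1 justifies 300 Stage 1 subjects by over 86% power for a gain of at least 6 points "from this pre-specified performance goal of 85" per cent, using a two-sided exact binomial test at 0.05. Section 16.1.3 carries the same benchmark to the pooled 600: "the lower bound of the 95% CI will be greater than 85% if the observed overall SVR12 rate is 88% or higher". Section 16.2 plans an analysis of Stage 1 and a final analysis of both stages together, so Stage 1 subjects enter both.

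Appendix IV, under the third amendment, gives the history of the goal: "overall SVR12 rate should be superior to 85% instead of the original 90% and an amendment was submitted accordingly". It identifies the change as "protocol v4.2, 05-October-2017 amendment 3" and gives reasons: a broad, difficult-to-treat population, published results for other treatments, and a WHO publication.

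Section 4.3 dates Stage 1: "Actual first enrollment: October 2016 in Malaysia, April 2017 in Thailand", and "Actual last visit completed (Follow-up visit Week 24): April 2018". Under the second amendment, of May 2017, Appendix IV gives the dates then planned: "Planned date of last visit completed for interim analysis: SVR4: July 2017, SVR12: November 2017". Section 9.2.1 states that the study is open label.

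**The concern.** The study has one regimen and no control group, so what it can claim depends on a benchmark fixed before the outcomes. Section 16.1.1 describes the Stage 1 goal as having that property, while the dated record in the same document shows that it does not. The amendment log matters here because it dates a property that the current text claims. That the log differs from the current text would not in itself be an error.

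At stake is how a result between the two goals is read. Someone who cites section 16.1.1 would present an interval just above 85% as meeting a goal set in advance, although the same interval would have missed the goal in force when those subjects enrolled.

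**Working it through.** **1. Were outcomes accruing on 5 October 2017?** SVR12 falls due 12 weeks after treatment, that is 12 + 12 = 24 weeks after the first dose without cirrhosis and 24 + 12 = 36 weeks with cirrhosis.

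- 5 October 2017 minus 168 days (24 weeks) is 20 April 2017.
- 5 October 2017 minus 252 days (36 weeks) is 26 January 2017.
- Subjects started by those dates had reached their nominal SVR12 date. Allowing the full +28-day visit window moves the dates back to 23 March 2017 and 29 December 2016.
- Malaysia enrolled from October 2016, so its first non-cirrhotic subjects were due from mid-March to mid-April 2017. Thailand enrolled from April 2017, so its first were due from mid-September to mid-October 2017.
- A week 24 follow-up visit falls 36 weeks (non-cirrhotic) or 48 weeks (cirrhotic) after the first dose. Counting back from the last one in April 2018, the last starts were about August and May 2017 respectively. Stage 1 had therefore probably finished enrolling before the change.
- The same visit implies that the last SVR12 visits fell about January 2018, so SVR12 was still incomplete at the change.

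**2. Reproducing the plan's figures.** The criterion is a Clopper-Pearson 95% lower limit above the goal p0: the 0.025 quantile of Beta(x, n − x + 1) exceeds p0, which is the same as P(X ≥ x | n, p0) < 0.025.

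- n = 300, p0 = 0.85: the smallest x is 268. P(X ≥ 268 | 300, 0.91) = 0.865, which matches the stated power of over 86%.
- n = 600, p0 = 0.85: the smallest x is 528, or 88.0% (interval 85.1% to 90.5%), which matches section 16.1.3.

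**3. The same criterion against both goals.**

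| n | Goal | Smallest x | Rate | 95% CI | P(X ≥ x) at the goal |
|---|---|---|---|---|---|
| 300 | 85% | 268 | 89.3% | 85.3% to 92.6% | 0.018 |
| 300 | 90% | 281 | 93.7% | 90.3% to 96.1% | 0.017 |
| 600 | 85% | 528 | 88.0% | 85.1% to 90.5% | 0.020 |
| 600 | 90% | 555 | 92.5% | 90.1% to 94.5% | 0.021 |

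Results that clear 85% but not 90% are 268 to 280 of 300 (280/300 = 93.3%) and 528 to 554 of 600 (554/600 = 92.3%).

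**4. Probability of clearing each goal.**

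| True SVR12 | n = 300, 85% | n = 300, 90% | n = 600, 85% | n = 600, 90% |
|---|---|---|---|---|
| 90% | 0.692 | 0.017 | 0.953 | 0.021 |
| 91% (design alternative) | 0.865 | 0.060 | 0.994 | 0.111 |
| 92% | 0.960 | 0.169 | 0.9997 | 0.360 |
| 95% | >0.999 | 0.881 | >0.999 | 0.997 |

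**The case against.** The 90% figure appears only in the amendment log, and the current text uses 85% consistently. The word *pre-specified* can be defended as meaning fixed before the Stage 1 analysis: amendment 3 came before the planned end of SVR12 visits (November 2017), the actual last visit (April 2018) and all Stage 2 enrolment (from January 2019). Appendix IV discloses the change, and section 16.1 repeats the external grounds for 85%. Section 16.2.4 states no success rule, so a change of verdict presumes a decision rule that the protocol does not set out.

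Much of this stands. It limits the point but does not make the label accurate. The Stage 1 goal was not fixed before those subjects enrolled or before the first of them reached SVR12, and disclosure in an appendix leaves the statistical section uncorrected.

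Three stronger readings are tempting, and the documents support none of them.

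- **That the goal was lowered because results were disappointing.** No aggregate look is recorded. The July 2017 SVR4 date is a planned visit date, and the footnotes to the visit schedules in section 7 have SVR4 RNA run on stored samples, so a visit is not a known result. The protocol does not say that those deciding were shielded from results. That silence proves nothing, since the SAP and the DSMB charter are not available here.
- **That the type I error is inflated.** The exact test of 85% keeps its nominal level, with upper-tail errors of 0.018 and 0.020. What changes is the claim being tested.
- **That Stage 2 alone is the proper test.** Section 16.2 plans no separate Stage 2 analysis. Stage 2 recruitment is steered to fill subgroups (section 8), and it excludes self-reported active injection drug use (section 5.3), so its population differs.

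**Conclusion.** The point holds in this form: for Stage 1 subjects, 85% was not set in advance, and section 16.1.1 should not say that it was. For Stage 2 subjects it was. The consequence is confined to observed rates of 89.3% to 93.3% in Stage 1 and 88.0% to 92.3% pooled. Outside those bands both goals give the same answer, and at a true rate of 95% with 600 subjects the change has almost no practical effect.

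The conclusion rests on these assumptions:

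- exactly 300 and 600 subjects in the analysis set;
- the lower-limit criterion inferred from sections 16.1.1 and 16.1.3;
- nominal treatment durations for the dates.

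The share of Stage 1 SVR12 results available on 5 October 2017 is unknown.

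**What to change.** 1. In section 16.1.1, replace the word *pre-specified* with a statement that amendment 3 changed the goal from 90% to 85% on 5 October 2017, during Stage 1. Give the reason, say what Stage 1 outcome data were known at that time and to whom, and refer to Appendix IV.
2. In the Stage 1 and pooled analyses, compare the exact 95% interval for SVR12 with both 85% and 90%.
3. State that 85% was set in advance only for Stage 2 subjects. A Stage 2 estimate may be shown as supportive, but not as the primary test.

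The cost is a few sentences and one further comparison of an interval already planned. The optional Stage 2 estimate would be an extra analysis. The downside is that a result inside the bands must be reported as meeting the amended goal but not the original one.

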16.1.3. Sample size determination for the global study

A total sample size of 600 patients will ensure that the width of the 95% CI around the overall SVR12 rate expected to be observed will be as small as 4-5% (see Figure 3). With this sample size, the lower bound of the 95% CI will be greater than 85% if the observed overall SVR12 rate is 88% or higher.

Figure 3: Confidence intervals for expected observed SVR12 rates in 300 and 600 subjects				
Observed overall	N=300		N=600	
SVR12 rate	95% CI	Width of 95% CI	95% CI	Width of 95% CI
87%	82.7% to 90.6%	7.9%	84.0% to 89.6%	5.6%
88%	83.8% to 91.4%	7.6%	85.1% to 90.5%	5.4%
89%	84.9% to 92.3%	7.4%	86.2% to 91.4%	5.2%
90%	86.0% to 93.2%	7.2%	87.3% to 92.3%	5.0%
91%	87.2% to 94.0%	6.8%	88.4% to 93.2%	4.8%
92%	88.3% to 94.8%	6.5%	89.5% to 94.0%	4.5%
93%	89.5% to 95.6%	6.1%	90.7% to 94.9%	4.2%
94%	90.7% to 96.4%	5.7%	91.8% to 95.8%	4.0%
95%	91.9% to 97.2%	5.3%	92.9% to 96.6%	3.7%

The study population will comprise up to 50% subjects with compensated cirrhosis. Based on preliminary site assessment, HIV/HCV co-infected subjects will represent approximately 30% of the study population. It is expected that 35-40% of the subjects will be infected by HCV genotype 3, 35-40% genotype 1, 15-20% genotype 6 and 5-10% genotype 2. In addition, a substantial fraction of the subjects may not be treatment naïve, and may have been previously exposed to interferon/ribavirin.

16.1.4. Sample size for the intensive PK substudy (Stage 1)

The sample size necessary to assess drug-drug interactions in HCV/HIV co-infected subjects will be also met. It is estimated that approximately one third of the subjects will be co-infected (see section 16.1.4).

In the intensive PK substudy (Stage 1), a total of 25 subjects will be enrolled in order to ensure adequate precision of PK parameter estimates. The precision required is a mean plasma ravidasvir AUC0-24h within $\pm 20\%$ of the true population mean (i.e. margin of error). The reported coefficient of variation (CV) of the AUC in HCV-infected adults for ravidasvir is 45.8% following multiple doses once daily. This is estimated to correspond to $\pm 2,800$ ng.hr/mL for a 200 mg daily dosing. Assuming the true mean and CV for the ravidasvir AUC0-24h are the same for Thai and Malaysian subjects as in the reported studies, the sample size calculation ensured that the 95% confidence interval of the sample mean for the AUC0-24h of ravidasvir is within $\pm 20\%$ of the true mean i.e. within $\pm 2,800$ ng.hr/mL.

Based on the reported variability at the standard dose and assuming mean AUC results are normally distributed, a sample size of 25 participants (taking into account 5-10% non-evaluable) is required. This sample size would also be sufficient to ensure the same precision for sofosbuvir and the sofosbuvir metabolite (GS31007) exposure based on the reported CV% for each drug (if also measured).

